4.3.2. Handling of Participant Withdrawals or Terminations

If a subject is withdrawn or discontinued from the study, the reason for withdrawal from the study is to be recorded in the source documents and on the CRF. All subjects withdrawn prior to completing the study should be encouraged to complete study procedures scheduled for the Month 12/Early Termination visit as soon as possible, and to return in 1 month for a Follow-up Visit. All AEs should be followed as described in Section 7. Subjects who discontinue or are withdrawn from the study will not be replaced.

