6.2. Study Schedule

This study is comprised of 9 clinic visits. Study assessments are to be performed according to the Schedule of Assessments and Procedures (Table 3). There is $a \pm 4$ -day window for each clinic visit.

The study will consist of a Screening Period (up to 2 months), a Pretreatment Period (1 week), a Treatment Period (12 months), and a Follow-up Visit (1 month). During the Treatment Period, subjects will have clinic visits for study-related protocol procedures at Day 1, Month 1, Month 3, Month 6, Month 9, and Month 12. The active phase of the study will be considered complete when the last subject undergoes the last visit. For the purpose of this study, 1 month is equal to 30 days.

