This study is being conducted during the COVID-19 pandemic. The COVID-19 outbreak emerged in December 2019 quickly became a global pandemic as declared by the World Health Organization in early March 2020. At that time, a variety of mitigations to assure safety of participants and address operational issues were implemented by Radius. To investigate the effect of the COVID-19 pandemic on study conduct, additional analyses comparing the subjects who completed or withdrew from the study before the onset of the COVID-19 pandemic, i.e, before 01 March 2020, with the subjects who were ongoing or randomized during the COVID-19 pandemic, i.e, on or after 01 March 2020, will be conducted where applicable.

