#### 3.12 Visit Windows

In general, the nominal visit will be used for the safety and efficacy data summaries and analyses.

During the COVID-19 pandemic, if a subject's DXA and/or QCT assessment cannot be performed during the protocol specified visit windows, the site will contact the study Medical Monitor and the subject will be allowed to make up the visits within an allowed time period. The allowable time period for collection of DXA and QCT assessments are shown in Table 3, where the ideal visit date is defined as the date that represents the ideal number of days from the date of first dose of study drug to the nominal visit.

Table 3:         Allowable Time Period for Collection of DXA and QCT Assessment
---

Visit	Ideal Visit Day	BMD or vBMD Assessment
Month 3	90	Up to 30 days after ideal visit day
Month 6	180	Up to 90 days after ideal visit day
Month 12	360	Up to 30 days after ideal visit day

Due to the expanded time periods for collection of efficacy assessments, analysis visit windows are defined below for the analyses of BMD, vBMD, and serum markers of bone metabolism (PINP and CTX) data to determine the assessment that will be used for a given study visit.

Table 4: Analysis V	Visit Windows	for BMD.	, vBMD, s	s-PINP and	I s-CTX.
---------------------	---------------	----------	-----------	------------	----------

Visit / Month	Allowable days from first dose of study drug			
	BMD lumbar spine, total hip and femoral neck, BMD Wrist	s-PINP, s-CTX	vBMD	
Visit 3 / Baseline	≤1	$\leq 1$	≤ 1	
Visit 4 / Month 1		2—60		
Visit 5 / Month 3	2—120	61—120		
Visit 6 / Month 6	121—270	121—270		
Visit 7 / Month 9				
Visit 8 / Month 12	≥ 271	≥271	≥2	

*Study BA058-05-019 SAP* 

It is possible that more than 1 assessment for a parameter may be obtained within the same analysis visit window. In such circumstances, the assessment with the date closest to the ideal visit day will be used. In the event that 2 assessments are equidistant to the ideal visit day, the later of the assessments will be used.

The analysis visit window convention will not be applied to the data listings. The data listings will display all data as collected with the corresponding nominal visit.

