- 1. Intermittent missing data in the placebo treatment group will be imputed using MCMC methods, assuming MAR. SAS PROC MI will be utilized for this step using the MCMC impute=monotone option. A total of 100 datasets will be created. These datasets will be utilized in Step #2.
- 2. The remaining missing values in the placebo group with a monotone missing data pattern will be imputed in this step. Missing data will be imputed assuming data are MAR. Only data (both observed and imputed) from subjects in the placebo group will be utilized in this step. SAS PROC MI will be used to impute missing values utilizing the monotone reg option. This will be performed for the 100 datasets. After this step, the 100 datasets will be fully imputed for the placebo treatment group.
- 3. The missing values at Month 12 in the abaloparatide-SC group will be imputed in this step. Control-based PMM imputation will be performed. With this imputation model, the missing values in the abaloparatide-SC group will not be constructed from the observed data in the abaloparatide-SC group but rather from the observed baseline and data (including imputed values) from the placebo group at Month 12. The MNAR statement in SAS PROC MI will be used to impute missing values. This will be performed for the 100 datasets.
- 4. A total of 100 fully imputed datasets will be created for both treatment groups. Since multiple imputation is a stochastic method, slight differences in output can be expected for different initial states of the random number generator. The seed numbers will be identified in the SAS programs to allow for reproducibility.

- 5. After the missing data imputation is completed using the above steps, percentage change values will be calculated in each of the imputed datasets at each visit.
- 6. These 100 datasets will be analyzed using ANCOVA models with fixed effect of treatment group and DXA instrument manufacturer, and baseline lumbar spine BMD as a covariate for the primary efficacy endpoint.
- 7. Treatment effects (difference in LS means between treatments) from these 100 analyses will then be combined using Rubin's Method via SAS PROC MIANALYZE procedure for the primary endpoint.

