The primary analysis using the PMM with the wash-out imputation method, and the other analyses using the MMRM model and the ANCOVA model using LOCF method, will be repeated using the PP population to support the findings from the ITT population.

For the primary efficacy endpoint using PMM analysis with wash-out imputation, subgroup analyses for each of the subgroups defined in Section 3.8 will be performed. The treatment groups will be compared within each subgroup. A forest plot of the estimated least square (LS) mean differences between the treatment groups (and corresponding 99% CIs) will be presented

by subgroup. Additional exploratory analyses examining subgroup effect and treatment by subgroup interaction may be performed, if warranted.

The efficacy analysis using MMRM model will also be repeated for the Antibody population, in which the subjects who are ADA+ at any post-baseline time point will be compared with subjects who are ADA- at all post-baseline time points. The MMRM model will include the fixed effects of ADA status, DXA instrument manufacturer, visit, and ADA status-by-visit interaction, with the baseline lumbar spine BMD as covariate.

To investigate the effect of the COVID-19 pandemic, the following sensitivity analyses will also be performed:

- a) PMM analysis with wash-out imputation for subjects who completed or withdrew from the study before 01 March 2020 and for subjects who completed or withdrew from the study on or after 01 March 2020. The analysis visit windows described in Table 4 will be used.
- b) PMM analysis with wash-out imputation using the nominal visit.
- c) PMM analysis with wash-out imputation excluding BMD measurements collected outside the allowable time period for data collection. In this analysis, BMD assessments are allocated to a Visit based on the inclusion rules shown in Table 5 below re: Sensitivity Analysis c).
- d) PMM analysis with wash-out imputation excluding BMD measurements which are more than 30 days after the ideal visit day. In this analysis, BMD assessments are allocated to a Visit based on the inclusion rules shown in Table 5 below re: Sensitivity Analysis d).

Visit	Ideal Visit Day	Sensitivity Analysis c): Allowable days from first dose of study drug	Sensitivity Analysis d): Allowable days from first dose of study drug
Month 3	90	2 —120 days	2—120 days
Month 6	180	121—270 days	121—210 days
Month 12	360	271—390 days	271—390 days

 Table 5:

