## Analyses of Key Secondary Efficacy Endpoints:

The primary population for the analysis of the key secondary efficacy endpoints will be the ITT population. The analyses will be performed using PMM analysis with wash-out imputation similar to the analysis model for the primary efficacy endpoint, with the appropriate baseline covariate.

Analyses of the primary and key secondary efficacy endpoints will follow a fixed-sequence testing approach to control the overall Type 1 error rate at the 2-sided significance level of 1%, as described in Section 3.7.

Sensitivity analyses using a MMRM model, sensitivity analyses for addressing the effect of the COVID-19 pandemic, and supportive analyses using LOCF method, as with the primary efficacy endpoint, will also be conducted. For the estimated treatment effects of the key secondary endpoints, 99% CIs will be presented together with the estimated p-values.

The analyses of each of the key secondary efficacy endpoints using the PMM method with washout imputation, the MMRM model, and the ANCOVA model using LOCF method will be repeated using the PP population to support the findings from the ITT population.

Subgroup analyses using PMM analysis with wash-out imputation will be performed on the key secondary efficacy endpoints using the ITT population for each of the subgroups defined in Section 3.8. The analyses will use analysis models as described above using the subset of ITT subjects belonging to the specific subgroup. A forest plot of the estimated least square (LS) mean

differences between the treatment groups (and corresponding 99% CIs) will be presented by subgroup for each of the key secondary efficacy endpoints.

The efficacy analysis using MMRM model for the key secondary endpoints will also be repeated for the Antibody population, in which the subjects who are ADA+ at any post-baseline time point will be compared with subjects who are ADA- at all post-baseline time points.

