#### Analyses of Additional Secondary Efficacy Endpoints:

All analyses performed for the primary efficacy endpoint for the ITT and PP populations will also be performed for all additional secondary efficacy endpoints involving the percent change from baseline in BMD parameters. The primary analyses will use the PMM analysis with washout imputation similar to the analysis model for the primary efficacy endpoint, with the appropriate baseline covariate. Sensitivity analyses, subgroup analyses, and other supportive analyses will be performed as described in Section 4.3.1; however, a two-sided alpha level of 0.05 will be used. For these analyses, 95% CIs for the estimated treatment effects will be presented along with the estimated p-values.

While no forest plot will be generated for the additional endpoints, LS mean ( $\pm$ SE) percent changes from baseline for lumbar spine, total hip, and femoral neck will be plotted by treatment group over time using the ITT population.

Percent (%) changes from baseline in BMD will be summarized using descriptive statistics by visit (Month 3, 6, and 12) for each treatment group. LS Mean ( $\pm$ SE) percent changes from baseline BMD will be plotted by treatment group over time using the ITT population.

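### COVID sensitivity analysis a) groups men by the date they left the study, which biases the pre-pandemic effect down and the pandemic effect up even if the pandemic did nothing (minor)

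*SAP*

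**What the plan says.** SAP 4.3.1 lists four COVID-19 sensitivity analyses of the primary endpoint. Analysis a) is a "PMM analysis with wash-out imputation for subjects who completed or withdrew from the study before 01 March 2020", with a companion analysis of men whose completion or withdrawal fell on or after that date. Analyses b) to d) change only which scans count for which visit, so a) is the only one of the four that separates men by period.

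The grouping carries over. For the key secondary endpoints SAP 4.3.2 plans "sensitivity analyses for addressing the effect of the COVID-19 pandemic, and supportive analyses using LOCF method, as with the primary efficacy endpoint". For the additional BMD percent-change endpoints, "Sensitivity analyses, subgroup analyses, and other supportive analyses will be performed as described in Section 4.3.1".

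Three other provisions matter:

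- **Imputation.** In step 3 of SAP 4.3.1, "the missing values in the abaloparatide-SC group will not be constructed from the observed data in the abaloparatide-SC group"; they come from baseline and placebo data.
- **Duration.** Protocol 6.2 gives "a Treatment Period (12 months), and a Follow-up Visit (1 month"), so a completer leaves at about 13 months.
- **Exit scans.** Protocol 4.3.2 says withdrawn men "should be encouraged to complete study procedures scheduled for the Month 12/Early Termination visit as soon as possible". That visit includes DXA (Protocol 6.2.13), and Table 4 of SAP 3.12 counts any scan from day 271 as Month 12.

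SAP 3.2 states the aim as "comparing the subjects who completed or withdrew from the study before the onset of the COVID-19 pandemic" with men ongoing or randomised during it.

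**The concern.** Whether a man falls before or after the cut depends partly on whether he drops out. Consider a man who started within about 13 months before 01 March 2020. If he stays, he is counted as 'after'. If he withdraws before the cut, he is counted as 'before'. Withdrawals are therefore concentrated in one group and depleted in the other.

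This matters because of the imputation rule. An abaloparatide man with no Month 12 scan is given a placebo-like value and contributes a treatment effect of roughly zero. More such men in 'before' pull its estimate down; fewer in 'after' push its estimate up. Placebo drop-outs are imputed from placebo under MAR and do not drive the offset.

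The analysis is meant to show whether the pandemic changed the treatment effect. The offset has the opposite sign to a pandemic loss of effect, so it makes such a loss harder to see. SAP 4.5.1 has explicit dose-counting rules for men treated across 01 March 2020, so the plan itself expects the men who create the problem.

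**Working it through.** **Inputs from the documents** (SAP 3.1): 225 men, 2:1; lumbar spine effect 6.5, SD 6.0; drop-out 10%; two-sided alpha 0.01. Key secondary effects: total hip 2.2, femoral neck 2.0. Completion at 13 months.

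**The plan's own figure.** The SAP gives none for analysis a), but its power statement reproduces. After 10% drop-out (135 and 67.5 men), SE = 6.0 × √(1/135 + 1/67.5) = 0.894; 6.5/0.894 − 2.576 = 4.69, so power is above 99.9%, consistent with the stated 99% or more.

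**Assumptions** (not in the documents): even enrolment over 24 months with the cut at month 18; drop-out times uniform over 12 months and equal in both arms; no pandemic effect; every drop-out after day 270 has an exit scan; an imputed abaloparatide man contributes zero effect and an observed man the full effect.

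**Step 1, who is 'before'.** Men enrolled in months 0–5 can have completed. Men enrolled in months 5–18 can be 'before' only as drop-outs.

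- 'Before' share = 5/24 × 0.9 + 6/24 × 0.1 + 12/24 × 0.05 = 0.2375, or 53 men.
- Drop-outs in it = 6/24 × 0.1 + 12/24 × 0.05 = 0.05, and 0.05/0.2375 = 21%.
- 'After' share = 0.7625, or 172 men; drop-outs 0.05/0.7625 = 6.6%.

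**Step 2, who is imputed.** Drop-outs after month 9 count as observed.

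- In 'before' these are 6/24 × 0.1 × 3/12 + 0.1 × 4.5/(12 × 24) = 0.0078, leaving (0.05 − 0.0078)/0.2375 = 17.8% imputed.
- In 'after' they are 0.025 − 0.0078 = 0.0172, leaving (0.05 − 0.0172)/0.7625 = 4.3% imputed.
- With groups fixed at entry, both have 10% × 9/12 = 7.5% imputed.

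**Step 3, expected effect** = true effect × share observed.

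| Endpoint, Month 12 | Before | After | Entry-date split, both groups |
|---|---|---|---|
| Lumbar spine (6.5) | 5.35 | 6.22 | 6.01 |
| Total hip (2.2) | 1.81 | 2.11 | 2.04 |
| Femoral neck (2.0) | 1.64 | 1.91 | 1.85 |

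If no late drop-out has an exit scan, the lumbar spine figures are 6.5 × (1 − 0.2105) = 5.13 and 6.5 × (1 − 0.0656) = 6.07, against 5.85 in both groups.

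**Step 4, precision.** With 2:1 allocation SE = 6.0 × √(4.5/n): 1.74 for 53 men and 0.97 for 172. The lumbar spine gap is 0.87 with SE √(1.74² + 0.97²) = 1.99.

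**Step 5, other calendars**, by simulation of the same model. The direction is the same in every row.

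| Enrolment length, cut at | Enrolment start to cut (months) | Gap | SE |
|---|---|---|---|
| 30 months, 90% | 27.0 | 0.50 | 1.70 |
| 30 months, 60% | 18.0 | 0.82 | 2.16 |
| 24 months, 90% | 21.6 | 0.67 | 1.74 |
| 24 months, 60% | 14.4 | 1.99 | 3.00 |
| 18 months, 90% | 16.2 | 1.24 | 2.06 |
| 18 months, 75% | 13.5 | 3.4 | 3.4 |
| 18 months, 74% | 13.3 | 3.9 | 3.7 |
| 18 months, 73% | 13.1 | 4.7 | 4.0 |
| 18 months, 70% | 12.6 | 5.7 | 4.5 |
| 18 months, 60% | 10.8 | 6.0 | 5.2 |

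In the last two rows nobody can have completed by the cut, so the 6 to 8 'before' men are all drop-outs. An entry-date split gives a gap of zero to within 0.01 wherever both of its groups contain men.

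**Earlier visits.** At Month 6 in the 24-month case, about 91% of 'before' and 98% of 'after' abaloparatide men are observed if every drop-out has an exit scan, and about 87% and 98% if none has.

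**The case against.** The best defence is that exit date is an exposure classification. The 'before' group holds exactly the men whose data the pandemic could not have touched, and SAP 3.2 says openly that this is the contrast intended. An entry-date rule blurs it, because some men then sit on the wrong side of the pandemic. This stands as a reason to keep the exit-date split as a description. It does not make two treatment effects comparable when their drop-out mix is set by the grouping rule.

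Second, nothing formal depends on analysis a). It lies outside the fixed sequence in SAP 3.7, and no test between the two groups is planned. That stands, and it is why the point is minor.

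Third, SAP 4.1 tabulates disposition by the same exit-date split and by randomisation date, and Protocol 4.3.1 has COVID-19 withdrawals recorded as such. A careful reader would see the drop-out imbalance. Those tables reveal it but do not correct the efficacy estimates.

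Three stronger readings are tempting, and the documents support none of them:

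- That analysis a) would hide or reverse a real pandemic loss. That depends on the size of the loss and on the enrolment calendar, and neither is given.
- That the offset is always lost in the noise. In most calendars tried it is inside its SE, but not when enrolment began about 11 to 13 months before the cut.
- That the primary result is affected. The primary analysis uses no exit-date grouping.

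**Conclusion.** The point holds as a minor one. The direction follows from the documents alone, provided that men were in the study on 01 March 2020 and that some abaloparatide men are imputed: 'before' is biased down and 'after' up, with unchanged drop-out and no pandemic effect.

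The size rests on assumed enrolment and drop-out patterns. For lumbar spine it is about 0.87 percentage points (SE about 2.0) in the 24-month case. Across 18 to 30 months of enrolment with the cut at 60–90%, it is about 0.5 to 2 in most calendars and inside its SE. It rises to about 3.4–6, and can exceed its SE, when enrolment began only about 11 to 14 months before the cut and the 'before' group is a handful of men who are mostly or all drop-outs. These SEs ignore imputation variance and covariate adjustment.

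With 225 men neither split could resolve a modest pandemic loss. That limits what analysis a) can show, but it is no reason to keep a directional bias that a change of definition removes.

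**What to change.** For analysis a) and its counterparts for the key secondary and additional BMD percent-change endpoints, define the groups by a date fixed at entry. The rule is scheduled Month 12 (first dose + 360 days, or randomisation + 360 days if never dosed) before, versus on or after, 01 March 2020. That amounts to a start before 07 March 2019 or not. Keep the exit-date split as a descriptive summary only. The randomisation-date split already in SAP 4.1 and 4.2 cuts at 01 March 2020 itself, which is a different division. Changing the safety summaries is optional.

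The cost is one SAP definition and one grouping flag, plus some blurring. In the 24-month case:

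- **360-day rule.** 'Before' has 6/24 × 225 = 56 men. About 12/24 × 0.05 × 225 = 6 men who withdrew before the pandemic fall in 'on or after'. About 1/24 × 0.9 × 225 = 8 men still in the follow-up month fall in 'before'. A few of those might have had a delayed Month 12 scan, since SAP 3.12 says "the subject will be allowed to make up the visits within an allowed time period", up to 30 days late at Month 12.
- **390-day alternative** (start before 05 February 2019). This removes the second group, apart from the follow-up visit window. It leaves 5/24 × 225 = 47 'before' men and about 7 early withdrawals in 'on or after', and the SE of the gap is 2.09 instead of 1.96.

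Either rule removes the offset. The choice should be written down before unblinding.

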## 4.3.2 Secondary Efficacy Endpoints

The key secondary efficacy endpoints are:

- Percent change from baseline in total hip BMD at 12 months
- Percent change from baseline in femoral neck BMD at 12 months.

Additional secondary efficacy endpoints are:

- Percent change from baseline in
  - Lumbar spine BMD at 3 and 6 months

- Total hip BMD at 3 and 6 months
- Femoral neck BMD at 3 and 6 months
- Ultra-distal radius BMD at 3, 6 and 12 months
- Distal one-third radius BMD at 3, 6 and 12 months.
- Log ratio of post-baseline over baseline in
  - s-PINP at 1, 3, 6 and 12 months
  - s-CTX at 1, 3, 6 and 12 months.
- Proportion of subjects experiencing BMD gains from baseline of >0%, >3%, and >6% at the lumbar spine, femoral neck, and total hip at 3, 6, and 12 months
- Incidence of new clinical fractures at 12 months
- Proportion of subjects converting from the categories of Osteoporosis to Osteopenia and Normal at end of treatment, where:
  - Osteoporosis is defined as lumbar spine or total hip BMD T-score  $\leq$  -2.5,
  - Osteopenia is defined as:
    - $\circ$  lumbar spine > 2.5 and total hip BMD T-score > -2.5 and < -1.0, or
    - $\circ$  lumbar spine > 2.5 and < 1.0 and total hip BMD T-score > -2.5,
  - Normal is defined as lumbar spine and total hip BMD T-score  $\geq$  -1.0.
- The percent change in total hip and femoral neck volumetric BMD as measured by quantitative CT (QCT) from baseline to 12 months. QCT will be performed in a subset of subjects at a selected number of study sites.

## Analyses of Key Secondary Efficacy Endpoints:

The primary population for the analysis of the key secondary efficacy endpoints will be the ITT population. The analyses will be performed using PMM analysis with wash-out imputation similar to the analysis model for the primary efficacy endpoint, with the appropriate baseline covariate.

Analyses of the primary and key secondary efficacy endpoints will follow a fixed-sequence testing approach to control the overall Type 1 error rate at the 2-sided significance level of 1%, as described in Section 3.7.

Sensitivity analyses using a MMRM model, sensitivity analyses for addressing the effect of the COVID-19 pandemic, and supportive analyses using LOCF method, as with the primary efficacy endpoint, will also be conducted. For the estimated treatment effects of the key secondary endpoints, 99% CIs will be presented together with the estimated p-values.

The analyses of each of the key secondary efficacy endpoints using the PMM method with washout imputation, the MMRM model, and the ANCOVA model using LOCF method will be repeated using the PP population to support the findings from the ITT population.

Subgroup analyses using PMM analysis with wash-out imputation will be performed on the key secondary efficacy endpoints using the ITT population for each of the subgroups defined in Section 3.8. The analyses will use analysis models as described above using the subset of ITT subjects belonging to the specific subgroup. A forest plot of the estimated least square (LS) mean

differences between the treatment groups (and corresponding 99% CIs) will be presented by subgroup for each of the key secondary efficacy endpoints.

The efficacy analysis using MMRM model for the key secondary endpoints will also be repeated for the Antibody population, in which the subjects who are ADA+ at any post-baseline time point will be compared with subjects who are ADA- at all post-baseline time points.

